2 STUDY OBJECTIVES

The objectives of the study and corresponding study endpoints are detailed in [Table 1](#).

Table 1: Objectives and Related Endpoints

Objective	Endpoint
Primary	
 To assess the safety and tolerability of TMP-301 following multiple ascending oral doses 
The primary endpoint is safety assessed after multiple-dose administrations by:
 
 Adverse events (AE) Clinical laboratory tests Vital sign measurements 12-lead electrocardiograms (ECG) Physical examinations Psychiatric assessments (Brief Psychiatric Rating Scale [BPRS], Clinician-Administered Dissociative States Scale [CADSS], Columbia Suicide Severity Rating Scale [C-SSRS], Modified Mini-Mental State Examination (3MS) and Alertness Visual Analogue Scale [VAS])
Secondary	
 To assess the pharmacokinetics (PK) profile of TMP-301 following multiple ascending oral doses 
 
 Day 1: Partial areas defined as AUC_{0-12} and AUC_{0-24}; maximum concentration (C_{max}), time of maximum concentration (T_{max}), concentration at 12 h (C_{12}), concentration at 24 h (C_{24}) where $C_{24} = C_{\text{trough Day2}}$ Day 14 (or last day of dosing): AUC_{ss} from time zero to the end of the (12 or 24 hour) dosing interval ($AUC_{0-TAU,ss}$). For BID cohorts, $AUC_{0-TAU,ss} = AUC_{0-12,ss}$, and for QD cohorts, $AUC_{0-TAU,ss} = AUC_{0-24,ss}$; $C_{avg,ss}$, $C_{max,ss}$, $T_{max,ss}$, $C_{12,ss}$, $C_{24,ss}$, and $C_{min,ss}$, all at steady-state (SS), along with apparent total plasma clearance (CL/F) and apparent volume of distribution (V_z/F) 

Exploratory	


 • To assess endpoints related to TMP-301 mechanism of action • To evaluate CYP1A2 genotypes and their association with phenotypes for potential impact on metabolism and to identify biomarkers of potential response to TMP-301. 	
Accumulation ratio derived as:
 
 • $AR_{AUC_{0-12}} = AUC_{0-12,ss} / AUC_{0-12, Day 1}$ • $AR_{AUC_{0-24}} = AUC_{0-24,ss} / AUC_{0-24, Day 1}$ • $AR_{C_{max}} = C_{max,ss} / C_{max,FD, Day 1}$ • $AR_{C_{12}} = C_{12,ss} / C_{12, Day 1}$ • $AR_{C_{24}} = C_{24,ss} / C_{24, Day 1}$ • Estimations of dose proportionality at steady State. Dose-normalized PK parameters (C_{max}, C_{12}, C_{24}, and AUC_{0-12} and AUC_{0-24}, when appropriate) will be assessed graphically for dose-proportionality For BID cohorts, $AUC_{0-TAU,ss} = AUC_{0-12,ss}$, For QD cohorts, $AUC_{0-TAU,ss} = AUC_{0-24,ss}$ • Estimation of time to achieve steady state (C_{trough} will be displayed graphically and summarized descriptively by day to assess for steady state) • As a marker of CYP1A2 activity, the ratio of paraxanthine to caffeine concentration (at 4 hours post caffeine dose) will be reported on Day -1 and Day 14. Change in CYP1A2 activity will be derived as $CYP1A2_ratio = \frac{\text{paraxanthine/caffeine concentration day 14}}{\text{paraxanthine/caffeine concentration day -1}}$
--	---

Abbreviations: AE = adverse event; ECG = electrocardiogram; PK = pharmacokinetics

3 STUDY DESIGN

3.1 General Description

This study will be a randomized, double-blind, placebo -controlled, fixed -sequence, MAD study. The study will be conducted in a single clinical research unit (CRU). The study will consist of up to 4 cohorts. Each cohort will consist of 8 subjects (6:2 for active: placebo), for a maximum total sample size of approximately 32 subjects. Subjects will only participate in 1 cohort.

Screening will occur within approximately 28 days prior to the first scheduled study drug administration. Screening data will be reviewed to determine subject eligibility. Subjects who meet all inclusion criteria and none of the exclusion criteria and who consent to participation will be admitted to the CRU for baseline evaluations prior to dosing. All baseline safety results should be available prior to the first study drug administration.

In cohort 2, subjects will be fasted overnight for 10 hours prior to the morning dose, followed by a 2 hour fast. Subjects were fasted for 2 hours prior to dosing and 2 hours following the evening dose for the cohort 1 (50 mg bid). If dosing in a fed condition is selected for cohort 3 or 4, subjects will be fasted overnight for approximately 9 hours, then given breakfast followed by study treatment dosing 30 minutes after initiation of breakfast.

Each subject will be randomly assigned to 1 of the following cohorts:

- Cohort 1:
 - Group 1 (6 subjects): 50 mg of TMP-301 bid
 - Group 2 (2 subjects): placebo (matching TMP-301) bid

- Cohort 2:
 - Group 3 (6 subjects): 50 mg of TMP-301 qd
 - Group 4 (2 subjects): placebo (matching TMP-301) qd

- Cohort 3:
 - Group 5 (6 subjects): Dose regimen of TMP-301 to be determined
 - Group 6 (2 subjects): placebo (matching TMP-301)

- Cohort 4:
 - Group 7 (6 subjects): Dose regimen of TMP-301 to be determined
 - Group 8 (2 subjects): placebo (matching TMP-301)

Safety will be assessed and blood samples for PK will be collected throughout confinement. Subjects will be discharged from the CRU on Day 18. Subjects will return to the CRU on Day 25 for a follow-up visit and End-of-Study (EOS) procedures.

Caffeine (100 mg) will be included as probe CYP1A2 substrate in cohort 2 and subsequent cohorts. Ratio of plasma paraxanthine/caffeine will be determined in a blood sample 4 hours after administration of caffeine at baseline (Day-1) and on day 14.

The maximum duration of subject participation, including Screening, will be approximately 53 days. Subjects who terminate the study early will perform follow-up procedures at the time of Early Termination.

Based on safety and tolerability findings in any of the cohorts, a 14-day dose titration cohort to evaluate the impact on treatment-emergent adverse events (TEAEs) may be added as an additional cohort (7 days titration + 7 days stable dosing).

3.2 Treatments

The following treatments will be administered according to [Table 2](#).

- IP: TMP-301 oral capsule
- Placebo: Matching placebo

Table 2: Dose Cohorts

Cohort	N (Active:Placebo)	Dose	Fasting Status	Drug Administration
1	6:2	Twice daily dose of 50 mg	Fasting Pre & 4 hours post dose	Twice daily TMP-301 or placebo dosing from Days 1 to 13 and once in the morning on Day 14 (for a total of 27 consecutive study drug administrations)
2	6:2	Once daily dose of 50 mg	Fasting Pre & 2 hours post dose or Fed 30 minutes pre-dose	or Once daily TMP-301 or placebo to be administered in the mornings of Days 1-14.
3 (Optional)	6:2	Dose and regimen to be determined		
4 (Optional)	6:2	Dose and regimen to be determined		

Caffeine (100 mg) will also be administered to enrolled subjects as part of the study on Day -1 and Day 14.

3.3 Study Procedures

For complete details on the study assessments to be performed for each cohort, refer to [APPENDIX A](#).

3.4 Randomization and Unblinding Procedures

3.4.1 Method of Assigning Subjects to Treatment Groups

Altasciences will generate the randomization code with a computer program according to the study design, the number of subjects and the number of treatments. Within each cohort, subjects will be randomized (3:1) to receive TMP-301 or placebo. The random allocation of each IP to each subject will be done in such a way that the study is balanced. Once generated, the randomization code will be final and will not be modified.

Subjects who sign the ICF and are randomized but do not receive the study treatment may be replaced. Subjects who sign the ICF, are randomized and receive the study treatment, and

subsequently withdrawn as a result of AEs thought to be related to the study drug will not be replaced. Subjects who sign the ICF, are randomized and receive the study treatment, and are subsequently withdrawn for reasons not related to the study drug may be replaced.

3.4.2 Blinding

The randomization code may be made available to the personnel of the bioanalytical facility. The treatment assignment will not be known by the study participants.

Furthermore, the randomization code will not be available to the physician and clinical staff involved in the collection, monitoring, revision, or evaluation of AEs, as well as clinical staff who could have an impact on the outcome of the study, and including the pharmacokineticist (or delegate), until database lock, or designation that unblinding information is required by the SRC to determine the next dose.

The preparation of the products will be done by designated personnel that are not directly involved in the clinical aspects of the trial.

The randomization code must not be broken except in emergency situations where the identification of a subject's study treatment is required by an Investigator for further treatment to the subject or to complete a SAE report. Randomization information will be held by designated individual(s). The date and reason for breaking the blind must be recorded.

The results of the PK analyses will be made available only to the personnel responsible for evaluating the safety data before proceeding with the next dose level.

3.5 Determination of Sample Size

No formal sample size analysis was performed. It is estimated that approximately 24 subjects should be sufficient to meet the objectives of the study.

4 ANALYSIS POPULATIONS

- **Enrolled Population**

The Enrolled population will include all subjects who signed the informed consent form (ICF).

- **Screened Population**

The Screened population will include all subjects who meet the eligibility criteria.

- **Randomized Population**

The Randomized population will include all subjects who are assigned a randomization number.

- **Safety Population**

The Safety population will include all subjects who received at least 1 dose of one of the investigational product (IP) or placebo. The number of subjects who were included, who discontinued, and who completed the study will be tabulated. The primary reasons for discontinuation will be provided.

- **Pharmacokinetic (PK) Population**

The PK population will include all subjects who have received at least 1 dose of the investigational product and have sufficient PK data to derive at least 1 PK parameter.

Subjects who do not complete the sampling schedule may be included in the PK analysis for only the PK parameters that are judged not to be affected by the missing sample(s).

5 DATA HANDLING AND PRESENTATION

All safety and statistical outputs will be generated using SAS software, version 9.4 or higher. The PK outputs will be generated using WinNonlin version 8.0 or higher.

All programs used to generate statistical analyses will be validated according to Altasciences' Standard Operating Procedures (SOPs).

The analyses described in this plan are considered a priori, in that they have been defined prior to database lock and prior to breaking the blind. Any analyses performed subsequent to database lock and breaking the blind will be considered post hoc and exploratory, and will be identified in the Clinical Study Report (CSR).

5.1 Safety Analysis Presentation

Adverse events and medical history will be classified using the Medical Dictionary for Regulatory Activities (MedDRA) terminology as defined in the study Data Management Plan (DMP).

Prior and concomitant medications will be coded with the World Health Organization Drug Dictionary (WHODrug) as defined in the study DMP.

In general, all safety summary tables will be presented for the Safety population. Summaries for AEs will be presented by treatment. Summaries for other safety endpoints will be presented by treatment if the endpoints are measured end of Study only.

In general, the data listings will include all subjects in the Randomized population up to the point of study completion or discontinuation; exceptions will be listings pertaining to a subset of subjects only (eg, subjects with protocol deviations) or a subset of records/events (eg, abnormal laboratory values). Limited data for those not included in the Randomized population, eg, who failed screening, may be presented, as appropriate.

Categorical variables will be summarized using number of observations (N), number of available data (n), and the percentage of available data (%) for each class. Continuous variables will be summarized using descriptive statistics, including N, n, arithmetic mean (mean), standard deviation (SD), minimum (min), median, and maximum (max).

The following general considerations may be applied:

- Study Day will be derived from the reference date (eg, the day of the first dose of study drug) and date of event as:
Study Day = (date of event – reference date) +1, if event is on or after the reference date;
Study Day = date of event – reference date, if event is before the reference date.
- Duration will be calculated using the general formula: (end date - start date) +1.
- If the reported value of a clinical laboratory parameter cannot be used in a statistical summary table (eg, a character string is reported for a parameter of the numerical type), a coded value may be appropriately determined and used in the statistical analyses. In general, a value below the lower limit of normal range such as ' <10 ' or ' ≤ 5 ' will be treated as half of the lower limit, '5' or '2.5', respectively, and a value above the upper limit of normal range such as ' >100 ' will be replaced with a number deemed

scientifically reasonable, eg, 101. However, the actual values as reported in the database will be presented in data listings.

- Unscheduled assessments will not be included in descriptive summary, except for baseline consideration. When assessments are repeated for a given time point or performed at unscheduled times, only the result which is the closest to the dosing time will be included in summary tables.

In general, summary statistics for raw variables (ie, variables measured at the study site or central laboratory) will be displayed as follows:

- Minima and maxima will be displayed to the same number of decimal places as the raw data
- Means, medians, and quartiles (if presented) will be displayed to 1 additional decimal place
- Standard deviations will be displayed to 2 additional decimal places
- Percentages will be displayed to 1 decimal place; Percentages between 0 and 0.1 (exclusive) will be displayed as '<0.1'
- P-values will be displayed to 3 decimal places; P-values that are less than 0.001 will be displayed as '<0.001'

Derived variables (ie, variables that are not measured by the study site but are calculated for analysis based on other measured variables) will be displayed with the same precision as the raw data, as appropriated, then follow the similar rules in presentation of summary statistics.

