ⁿ Days 1 and 7: Prior to morning dosing and 0.5, 1.00, 2.00, 3.00, 4.00, 6.00, 8.00, and 12.00 hours. Days 2, 4, 6, 8, 10, and 12: Prior to dosing and 4.00 and 12.00 hours postdose. Day 14: Prior to dosing and 0.5, 1.00, 2.00, 3.00, 4.00, 6.00, 8.00, 12.00, 24.00 (Day 15), 48.00 (Day 16), 72.00 (Day 17), 96.00 (Day 18) hours postdose.

^o At baseline on Day 1, predose vital sign measurements (except oral body temperature) will be conducted in triplicate (with an interval of approximately 10 - 30 minutes between each recording). The average value of each parameter will be considered as baseline value.

^p Symptom-directed physical examination.

^q Days 1 and 7: Predose and at 4.00, 6.00, 8.00, and 12.00 hours postdose. Days 2, 4, 6, 8, 10, and 12: Predose and 4.00 and 12.00 hours postdose. Day 14: Prior to dosing and 0.5, 1.00, 2.00, 3.00, 4.00, 6.00, 8.00, 12.00, 24.00 (Day 15), 48.00 (Day 16), 72.00 (Day 17), 96.00 (Day 18) postdose.

^r At baseline in Day 1 predose, ECG recordings will be conducted in triplicate at (-45, -30, and -15 minutes). The average value of each parameter will be considered as baseline value.

^s Day 1, 7, and 14: Predose then 4.00, 6.00, and 12.00 hours postdose and Day 18.

^t May also be conducted at other times if deemed appropriate based on emerging data.

^u Check-in, then 6.00 and 24.00 hours postdose on Day 1, Day 7, and Day 14.

^v Conducted as part of the psychiatric examination.

^w Check-in , and 24.00 hours postdose on Day 1, Day 7, and Day 14.

^x Subjects will be screened within 28 days prior to dosing. A psychiatric examination will be performed at Screening by a suitably trained psychiatrist or appropriately trained staff using a clinical interview. This will include an assessment of premorbid personality, personal and developmental history, alcohol and substance use history, forensic history, past psychiatric history, and mental state examination.

^y Every other day from Day 1 to discharge.

^z Approximately 1 week after last dose.

^{aa} 96 hours after the last (Day 14) dose

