9 PSYCHIATRIC ASSESSMENTS AND ANALYSIS

Unless otherwise specified, all available psychiatric assessments and analysis will be presented for the Safety population. Listings will be based on the Randomized population.

Missing data for subjects who are administered all scheduled study treatments will be considered as random non-informative missing for analysis purposes. Missing values will be examined on a case-by-case basis to confirm this. Reasons for missing data will be displayed in the listings. No further imputation will be applied to any missing values.

Assessments done outside the acceptable visit windows may be excluded from by-time point summary statistics; this will be determined on a case-by-case basis prior to unblinding.

Analyses will be based on actual assessment times, except for predose (baseline) times, which will automatically be considered as time 0 as appropriate for analysis. If the actual time is missing, the nominal time will be used.

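### SAP 5.1 contradicts itself on unscheduled assessments and no worst-postdose summary is planned, so BPRS, CADSS and 3MS scores prompted by an event may appear only in listings

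*SAP*

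**What the plan says.** Among points introduced by "The following general considerations may be applied", SAP 5.1 has a bullet of two sentences. The first reads: "Unscheduled assessments will not be included in descriptive summary, except for baseline consideration". The second concerns assessments repeated at a time point or done off schedule; of these, "only the result which is the closest to the dosing time will be included in summary tables".

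For BPRS, CADSS and 3MS, SAP 9.1.3, 9.2.3 and 9.4.3 define only change and percent change in total score at each postdose time point. Maximum and minimum postdose effects (E_max, E_min) are defined for the Alertness VAS alone (SAP 9.5.2). SAP 9.6 summarises scores by time point and fits a mixed model to the change endpoints. It does not say whether unscheduled scores enter that model.

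The protocol foresees extra scoring. Footnote t of Protocol Table 3, attached to the VAS, BPRS, CADSS and 3MS rows, says: "May also be conducted at other times if deemed appropriate based on emerging data". Footnote c allows a psychiatric examination at any time if there is a relevant concern, and footnote v makes BPRS, CADSS and 3MS part of the psychiatric examination.

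**The concern.** The psychiatric scales are named components of the primary safety endpoint (SAP Table 1), and Protocol Appendix 14 names dissociation and hallucination as risks of the drug class. A score taken because someone was worried about a subject is the one a reader of the scale tables most needs to see. Under the first sentence it is left out of those tables. Under the second it may be admitted, but only if it is nearest to dosing, and the sentence does not say under which time point it would be shown. With no worst-value summary for BPRS, CADSS or 3MS, no other planned table on these scales is certain to show it.

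**Working it through.** The plan states no figure on this point, so there is none to reproduce.

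**1. The two sentences side by side.** Take an unscheduled postdose BPRS on Day 4.
- First sentence: excluded, because it is not a baseline value.
- Second sentence: eligible if it is the result closest to dosing, but there is no scheduled Day 4 time point to hold it.

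Take instead a 6 h assessment repeated at 8 h with a higher score. The second sentence keeps the 6 h value. Selection is by time and never by score.

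**2. Time between scheduled scores.** Inputs: BPRS and CADSS at 6 h and 24 h after dosing on Days 1, 7 and 14 (Protocol Table 3, footnote u). Hour 0 is the Day 1 dose, so a score falls at (day − 1) × 24 + h.
- Day 1: 6 and 24 h
- Day 7: 144 + 6 = 150 h and 144 + 24 = 168 h
- Day 14: 312 + 6 = 318 h and 312 + 24 = 336 h

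The long gaps are 150 − 24 = 126 h and 318 − 168 = 150 h. Together they make 276 h, and 276/336 = 82%.

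For 3MS (24 h after dosing on the same days, footnote w) the scores fall at 24, 168 and 336 h, with gaps of 144 h and 168 h.

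Sensitivity: SAP 9.2.1 and 9.4.1 also mention predose CADSS and 3MS on Days 7 and 14, which the footnotes do not. If those were done, at 144 and 312 h, the long gaps would be 144 − 24 = 120 h and 312 − 168 = 144 h. That is 264 of 336 h, or 79%, so the conclusion is unchanged.

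**3. Size of one omitted score (illustration).** Inputs: 6 active subjects per cohort (SAP 3.1); 18 as the score expected of a healthy volunteer and 25, 31, 41 and 53 as cutoffs (SAP Table 5, BPRS Details). Using the cutoffs as event scores is an assumption. So is a score of 18 for the other five subjects, and for the affected subject at every scheduled time. The fall in the mean when the event score s is replaced by 18 is (s − 18)/6.

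| Assumed event score | Fall in cohort mean | Maximum with → without |
|---|---|---|
| 25 | 7/6 = 1.2 | 25 → 18 |
| 31 | 13/6 = 2.2 | 31 → 18 |
| 41 | 23/6 = 3.8 | 41 → 18 |
| 53 | 35/6 = 5.8 | 53 → 18 |

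**The case against.** The strongest reply is that the event is reported elsewhere. It would be in the adverse event tables by system organ class, preferred term and severity. A psychiatric emergency is a serious adverse event by definition (Protocol 7.6), and the scale values are listed. This stands: nothing disappears from the study report. But those tables give incidence and severity grade, not the size of the change on the scale.

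Four further points are fair.
- The rules in SAP 5.1 are permissive, and an event lasting until a scheduled 6 h or 24 h score is tabulated. BPRS item 12 also looks back a week, so hallucinations in a gap could be rated at the next scheduled score. That is one item of 18.
- Footnote t can be read as allowing a change of schedule rather than scoring prompted by one subject. Footnotes c and v support the latter better, though not for the VAS.
- Appendix 14 requires the investigator to evaluate a suspected psychiatric event and does not mandate rescoring, so an unscheduled score may not exist.
- The VAS already has E_max and E_min, so it lacks only a statement on unscheduled records.

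Three stronger readings are tempting. A reader might infer that event scores can never reach the tables; the second sentence and the permissive wording rule that out. A reader might also infer that an event on a day without a scheduled score can be captured only by unscheduled scoring; persistence and look-back rule that out. Finally, a reader might infer that SAP 9 removes such scores by treating missing data as non-informative. It does not: "Missing data for subjects who are administered all scheduled study treatments will be considered as random non-informative missing for analysis purposes", and the SAP adds "Missing values will be examined on a case-by-case basis to confirm this". An assumption about missing values discards no score that was collected, and a subject stopped early lies outside it.

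**Conclusion.** The concern holds as a contradiction in SAP 5.1 combined with a missing summary. Whether an event-prompted score is tabulated is left undetermined in a plan that calls its analyses a priori (SAP 5). If the first sentence governs, such BPRS, CADSS and 3MS scores are found only in listings.

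The 82% describes the schedule. It is not the probability that an event is missed, which depends on how long events last and whether anyone rescores the subject. The 1.2 to 5.8 points rest on assumed scores and show the scale of what one record can change in a cohort of six; they do not estimate bias in a planned statistic. The effect is confined to the scale summaries. It does not show that the overall safety conclusion would be biased, because adverse event reporting is untouched. The change is worth making because it is cheap and concerns a named primary safety measure.

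**What to change.** In the SAP:
1. Reconcile the two sentences in 5.1, and keep by-time-point tables on scheduled values.
2. Add for BPRS, CADSS and 3MS each subject's worst postdose score and worst change from baseline, by treatment and with individual values. For 3MS the worst is the lowest score. Use all postdose records, including unscheduled ones and any collected after early discontinuation. Protocol Table 3 shows none of these scales at discharge or follow-up, so such late records may be few.
3. State that VAS E_max and E_min include unscheduled records.
4. State whether unscheduled scores enter the mixed model in 9.6.

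The cost is SAP wording and one extra summary per scale, from data that would already be in the database. The drawback is that subjects assessed more often have more chances of an extreme value, so the number of records per subject should be shown beside the worst value.
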